## 2. STUDY PURPOSE AND RATIONALE

HCT recipients are most vulnerable to infection during the early post-transplant period; however, active immunization against SARS-CoV-2 is thought to be ineffective during this period because all patients continue on immunosuppressive medications to prevent graft-versus-host disease (GVHD) and the immune system is not yet fully reconstituted(18, 19). In addition, most HCT recipients lose their immunity to various pathogens as soon as during the first months after transplant, irrespective of pre-transplant donor or recipient vaccinations. Current guidelines recommend considering vaccination at least three months

after transplant even though efficacy is unknown and may be sub-optimal. Passive immunization with monoclonal antibodies (mAbs) against SARS-CoV-2 administered pre-transplant represents a strategy to reduce the risk of COVID-19 among HCT recipients this the period of vulnerability when vaccination is not recommended or when vaccine responses may be sub-optimal.

This is a prospective, open-label phase 1 clinical trial that will enroll hematopoietic stem cell transplant candidates to receive the mAb VIR-7831 targeting SARS-CoV-2. The primary objective is to assess the pharmacokinetics of this extended half-life mAb post-transplant.

Previous studies have found that the half-life of CMV- and RSV-specific antibodies is 7-10 days in HCT recipients which is significantly less than the 21-day half-life of IgG in healthy adults(20-22). Although the mechanism of this accelerated decay is unclear, one possible explanation is increased antibody loss through graft versus host disease (GVHD)-related gut leakage which may be more common among recipients of mis-matched unrelated donor stem cell transplants. Monoclonal antibodies against SARS-CoV-2 administered pre-transplant represent a strategy to reduce the risk of COVID-19 among HCT recipients. This study will assess the pharmacokinetics of one such monoclonal antibody with regards to half- in the serum in both autologous and allogeneic transplant recipients. As an exploratory analysis, nasal antibodies may also be measured to determine the bioavailability of VIR-7831 in the nose since this is the portal of entry for infection by SARS-CoV-2.

The paired collection of blood by venipuncture and TASSO will also provide information about how antibody levels correlate between the two collection methods and if a correction factor needs to be applied to the TASSO results. Preliminary and published data suggest high concordance rates in antibody levels as measured from capillary blood versus venous blood samples(23, 24). This information will help determine the half-life of VIR-7831 when blood is self-collected by TASSO alone after day +100 post-transplant when patients are followed less closely by the transplant service.

Overall, a better understanding of the kinetics of antibody decay in the serum could help determine the utility of immunoprophylaxis in bridging this window of vulnerability among HCT recipients. If the half-life of mAbs like VIR-7831 is diminished in allogeneic transplant recipients, re-dosing may need to be considered in order to bridge the entire window of vulnerability to SARS-CoV-2 post-transplant. If the half-life of mAbs is not altered in autologous transplant recipients, redosing may not be needed in this population.

### **3. STUDY OBJECTIVES**

#### **3.1 Primary Objective**

To determine the levels of VIR-7831 mAb post-transplant in serum over time.

#### **3.2 Secondary Objectives**

1. To compare the half-life of VIR-7831 in autologous vs. allogeneic transplant, cord vs. non-cord allogeneic transplant, matched vs mis-matched donors, in patients with and without GVHD, and in patients with and without diarrhea

2. To monitor the frequency of breakthrough SARS-CoV-2 acquisition in HCT recipients who have received VIR-7831
3. To compare antibody levels from serum collected by venipuncture versus self-collected using a TASSO device.
4. To monitor the development of anti-drug antibodies
5. To monitor safety
6. Exploratory: To measure VIR-7831 and SARS-CoV-2 neutralizing antibodies in nasal swabs and SARS-CoV-2 neutralizing antibodies in serum.

### 3.3 Projected Target Accrual

[figure not shown]
Table 1: Targeted / Expected Enrollment: HCT candidates			
Ethnic Category	Patient Numbers		
	Females	Males	Total
Hispanic or Latino	1	1	2
Not Hispanic or Latino	19	29	48
Ethnic Category Total of All Subjects*	20	30	50
Racial Category			
American Indian / Alaska Native	0	0	0
Asian	1	1	2
Native Hawaiian or Other Pacific Islander	0	0	0
Black or African American	1	1	2
White	18	27	45
More than One Race	0	1	1
Racial Categories: Total of All Subjects*	20	30	50

## 4. STUDY DESIGN AND INVESTIGATIONAL PLAN

This is a prospective, open-label, phase 1 clinical trial of a mAb administered intravenously to HCT candidates within seven days prior to the start of conditioning for transplant. The target enrollment for this trial is 50 HCT candidates. Twenty subjects have already been infused with a 500 mg dose. Thirty additional subjects will be infused with the 2,000 mg dose. The study is open to anyone regardless of gender or ethnicity.

## 4.1 Overall Study Design

**Figure 1: Overview of study design and timeline.**

Participants will be screened, consented, and enrolled prior to transplant. Clinical evaluation will occur immediately prior to mAb administration. Participants will complete a weekly symptom questionnaire prior to and weekly after mAb administration for a total 36 weeks. Safety assessments will be performed with routine labs as part of standard stem cell transplant care. mAb will be administered intravenously within seven days of the start of conditioning, and the mAb will be infused at least 24 hours prior to the start of conditioning, i.e. mAb infusion will occur within 1-7 days prior to conditioning. Immediately prior to mAb administration (Pre), at the end-of-infusion (\* in the schematic), weekly up to week 4, monthly up to week 12, and at week 24 after mAb administration, blood will be collected by venipuncture or from a central venous catheter if one is available (10-20 mL per blood draw). At week 12, and monthly thereafter to the end of the primary end-point (week 24), blood will be self-collected using a TASSO device if the participant is unable to return for a venous blood draw. Each timepoint for blood collection will utilize two TASSO devices (or one TASSO+ device). If a participant can present in clinic or is in the hospital, blood collection by venipuncture or from a central venous catheter is permitted instead of using a TASSO device. Nasal specimens will be collected by mid-nasal foam swab at the same time-points as blood draws for antibody testing. Additional nasal swabs may also be collected off-schedule as needed based on reporting of respiratory symptoms on the weekly questionnaire, up to week 36. If positive for SARS-CoV-2, weekly nasal swabs will be obtained longitudinally for SARS-CoV-2 PCR until negative or until week 36. If a participant can present in clinic or is in the hospital, blood can be collected by venipuncture or from a central venous catheter instead of by a TASSO device. Routine nasal swabs collected as part of standard clinical care for SARS-CoV-2 surveillance by PCR post-transplant are not shown. At week 36 (not shown), participants will receive a follow-up phone call to assess for the development of antibody dependent enhancement if they had COVID-19.

## 4.2 Protocol Enrollment

Enrollment is expected to take approximately 6-12 months. The duration of a participant's involvement with the study is expected to be approximately 24 weeks for the primary end-point with a follow-up call at week 36 to assess for antibody dependent enhancement. The study will be introduced to HCT candidates during intake or at transplant arrival at which time interested participants can contact the study team to discuss participation and to schedule a screening visit.

## 5. STUDY POPULATION

### 5.1 Inclusion Criteria, HCT candidates

Participants must meet all the following criteria to be eligible for the study:

#### Informed Consent and Willingness to Participate

- 1) Patients (or legally authorized representative if applicable) must be capable of understanding and providing a written informed consent

#### Age Criteria

- 2) Patients must be at least 18 years of age, of any gender, race, or ethnicity.

#### Nature of Illness and Treatment Criteria

- 3) Patients must be undergoing HCT (any donor or stem cell source including autologous or cord blood)
- 4) History of prior transplants are permitted
- 5) History of COVID-19, history of vaccination for SARS-CoV-2, positive PCR of a respiratory specimen for SARS-CoV-2 as long as it is not within four weeks from conditioning, or seropositivity for SARS-CoV-2 are permitted
- 6) History of SARS-CoV-2 infection or vaccination of the donor are permitted.
- 7) Post-enrollment vaccination is anticipated and permitted
- 8) Administration of IVIG before or during the study is permitted

### 5.2 Exclusion Criteria, HCT candidates

Participants who meet any of the following criteria will not be eligible for the study:

#### Other illnesses or conditions

- 1) Signs or symptoms of uncontrolled, active infection
- 2) Positive PCR result for SARS-CoV-2 within four weeks of scheduled conditioning
- 3) Pregnant or breastfeeding (this population is generally not cleared for transplant)
  - o Pregnancy test is obtained as part of pre-transplant evaluation in women of child-bearing potential at arrival to transplant and again within 7 days of conditioning and will be confirmed as negative by review of the chart
- 4) Previous anaphylaxis or severe hypersensitivity reaction, including angioedema, to a mAb
- 5) Previous reaction to a mAb that required medical attention
- 6) Participants of other clinical studies that preclude the use of other investigational compounds
- 7) Participants who, in the judgment of the investigator, will be unlikely or unable to comply with the requirements of the protocol or unlikely to survive to the end of study

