**Patient Exclusion Criteria:**

- Positive PCR result for SARS-CoV-2 within four weeks of scheduled conditioning
- Signs or symptoms of uncontrolled active infection
- Pregnant or breastfeeding
  - Pregnancy test is obtained as part of pre-transplant evaluation in women of child-bearing potential at arrival to transplant and again within 7 days of conditioning and will be confirmed as negative by review of the chart
- Previous known allergies to any component of VIR-7831
- Previous anaphylaxis or severe hypersensitivity reaction, including angioedema, to a mAb
- Participants of other clinical studies that preclude the use of other investigational compounds
- Participants who, in the judgment of the investigator, will be unlikely or unable to comply with the requirements of the protocol or unlikely to survive to the end of study

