## 6. TREATMENT PLAN

### 6.1 VIR-7831 administration

VIR-7831 will be given intravenously as a single dose of 2,000 mg infused over approximately 60 minutes. A 500 mg single dose was used in the phase 3 COMET-ICE study and is the dose authorized under the EUA for early treatment. However, the 500 mg dose has reduced *in vitro* neutralization potency against the Omicron BA.2 subvariant which has emerged as the predominant variant of SARS-CoV-2 in the United States. An increased dose of 2,000 mg is predicted to rescue neutralization potency against Omicron BA.2 and will be used for the remaining 30 subjects in this study. A lead-in phase will consist of the first ten participants infused with the 2,000 mg dose. Lead-in phase participants will have a 120-minute post-infusion observation period, which is increased from the 60-minute monitoring period used for the previous 20 participants who received the 500 mg dose. If no infusion-related reactions (grade 3 or above) or serious adverse events are noted between 60-120 minutes post-infusion, the monitoring period may be shortened to 60 minutes. The mAb will be administered within seven days prior to the planned start of pre-transplant conditioning, and the mAb will be infused at least 24 hours prior to the start of conditioning, i.e. mAb infusion will occur within 1-7 days prior to conditioning). If conditioning is unexpectedly delayed by > 14 days after administration of VIR-7831, the subject can stay in the study but will not count towards the target sample size and will be excluded from the primary analysis. This would allow continued safety monitoring and analysis of secondary and exploratory objectives. Vials with the mAb will be stored between 2 and 8°C in the investigational drug service (IDS) pharmacy at FHCC.

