## **8. INFORMED CONSENT OF SUBJECT**

Potentially eligible participants will be pre-screened and they or their legally authorized representative contacted to establish interest in the study. If interested, we will arrange a consent meeting in person during a video or phone call based on the preferences of the patient.

The key information about the purpose of the study, the procedures and experimental aspects of the study, the risks and discomforts, and alternative treatment will be presented to the participant.

Participants will be given sufficient time to consider participation in the study. Participants will be asked to sign the consent prior to starting any study procedures. Consent from the patient will be obtained using forms approved by the Fred Hutchinson Cancer Center Institutional Research Board (FHCRC IRB). Once signed, a copy of the informed consent form will be given to the participant for their records. Participants may withdraw consent at any time throughout the course of the study. The rights and welfare of the subject will be protected by emphasizing to them that the quality of medical care will not be adversely affected if they decline/withdraw from the study.

Patients will initially be screened prior to their scheduled transplant. Enrollment will occur when data are reviewed for all inclusion and exclusion criteria by the study and the participant signs consent for infusion. A unique study number will be allocated to each patient and a log of enrolled patients will be maintained.

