### Medical records:

Medical records from the University of Washington, outside health care providers, and databases maintained by the Fred Hutchinson Cancer Center will be reviewed for data such as subjects' demographics, underlying malignancy, treatment, and medical history with a focus on HCT related treatment and disease response.

- At screening, these include review of standard pre-transplant medical history and labs to assess inclusion/exclusion criteria:
  - Age
  - Underlying disease
  - HCT planned type and date
  - History of prior transplants

- History of COVID-19, positive PCR of a respiratory specimen for SARS-CoV-2 as long as it is not within four weeks from conditioning, or seropositivity for SARS-CoV-2
  - History of SARS-CoV-2 infection or vaccination of the donor
  - Ability to provide informed consent
  - Prior administration of IVIG
  - Pregnancy test results
  - Previous known allergies to any component of VIR-7831
  - Previous anaphylaxis or severe hypersensitivity reaction, including angioedema, to a mAb
  - Participation in other clinical studies that preclude the use of other investigational compounds
- On the day of infusion, at the end-of-infusion, weekly to week 4, and monthly to week 24, these include review of the medical history with regards to underlying disease, medications, history of infections, history of vaccinations, and presence/severity of GVHD. In addition, standard post-transplant laboratory testing which are collected as follows from Day 0 to +100 post-transplant and as clinically indicated thereafter will be reviewed, including:
  - CBC daily until granulocytes > 500 cells/mm^3 and platelets > 20,000 cells/mm^3, then a CBC a minimum of once weekly until 100 days post-transplant.
  - Electrolytes, glucose, creatinine, BUN, every day as inpatient. At the ambulatory clinic, electrolytes are monitored a minimum of once per week.
  - Ca++, Mg++, PO4, albumin, twice a week as inpatient. At the ambulatory clinic, they are monitored a minimum of once per week
  - Bilirubin [total/direct], AST, alkaline phosphatase, LDH, a minimum of two times a week as inpatient. At the ambulatory clinic, monitoring is as follows: – If LFT's elevated: twice weekly.
  - INR is monitored weekly for patients on prophylactic Warfarin.
  - Blood cultures (aerobic and anaerobic) are obtained from patients receiving > 0.5 mg/kg/day of prednisone or prednisone equivalent. Twice weekly when inpatient.

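### The more recent of the two pregnancy tests behind exclusion 3 is timed to conditioning, and nothing places it before the VIR-7831 infusion, which comes 1 to 7 days before conditioning

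*Combined protocol and SAP*

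**What the plan says.** Section 5.2, exclusion 3, bars pregnant or breastfeeding patients. For women of child-bearing potential it relies on testing from the pre-transplant evaluation, obtained "at arrival to transplant and again within 7 days of conditioning and will be confirmed as negative by review of the chart". The Synopsis (Patient Exclusion Criteria) gives the same rule: "again within 7 days of conditioning and will be confirmed as negative by review of the chart".

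The study drug is also timed to conditioning. Section 6.1 says "mAb infusion will occur within 1-7 days prior to conditioning", and the Synopsis (Study Population) and Section 4.1 agree. Sections 6.1 and 11 also foresee late slippage: "If conditioning is unexpectedly delayed by > 14 days after administration of VIR-7831, the subject can stay in the study".

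Three places bear on when eligibility is settled:

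- Section 8: "Enrollment will occur when data are reviewed for all inclusion and exclusion criteria by the study and the participant signs consent for infusion".
- Section 9.1, Medical records: "At screening, these include review of standard pre-transplant medical history and labs to assess inclusion/exclusion criteria". The list that follows includes "Pregnancy test results", with no date limit relative to infusion.
- Appendix A: the inclusion/exclusion row is marked once, at screening. There is no pregnancy row and no eligibility recheck on day 0 before infusion.

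**The concern.** The exclusion governs exposure to VIR-7831, but the second test is anchored to a later event, the start of conditioning. A participant could be infused 7 days before conditioning and have the second test 3 days before conditioning. That sequence meets the timing in Section 5.2 and in Section 6.1, yet only the arrival result existed at dosing. The documents give no interval between arrival and infusion, so the age of that result is not bounded.

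What is at stake is when a pregnancy would be found. The dose is single and cannot be withdrawn, and Section 12.3 anticipates a half-life of up to 3 months. Found before infusion, a pregnancy is a screen failure. Found by a test after infusion, it is a study exposure, with notification within 24 hours and follow-up to 1 year after birth (Section 10.4.1, Reporting to GSK and Vir).

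**Working it through.** The plan states no figure on this point, so there is none to reproduce. The check counts permitted day combinations and then reads the eligibility sections against each other.

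**Inputs**

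- Infusion k days before conditioning, k = 1 to 7 (Section 6.1).
- Second test j days before conditioning, j = 1 to 7 (Section 5.2). This assumes that the phrase in Section 5.2 means the 7 days before conditioning. A variant also allows the day conditioning starts, j = 0.

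The test follows the infusion when j < k.

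**Count, test on days -7 to -1**

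- Total pairs: 7 × 7 = 49.
- Test after infusion: sum of (k − 1) over k = 1 to 7 = 0+1+2+3+4+5+6 = 21.
- Same day: 7.
- Test before infusion: sum of (7 − k) = 6+5+4+3+2+1+0 = 21.
- Check: 21 + 7 + 21 = 49.

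**Count, test on days -7 to 0**

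- Total pairs: 7 × 8 = 56.
- Test after infusion: sum of k over k = 1 to 7 = 28.
- Same day: 7. Before: 21.
- Check: 28 + 7 + 21 = 56.
- For an infusion on day -7, 7 of the 8 permitted test days come after it.

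**Eligibility sections side by side**

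| Place | What it fixes | What it leaves open |
|---|---|---|
| Synopsis, Section 5.2 | Tests at arrival and near conditioning; negative result confirmed in the chart | Whether the second result precedes the infusion |
| Section 6.1 | Infusion 1 to 7 days before conditioning | Any link to the pregnancy result |
| Section 8 | All criteria reviewed at enrollment | How to review a test that Section 5.2 allows to be taken later |
| Section 9.1 | Pregnancy results reviewed at screening | Which result, and how old |
| Appendix A | Eligibility assessed at screening | Any check between screening and infusion |

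Under a strict reading of Section 8, both results must be in hand before enrollment, and so before dosing. Under the wording of Section 5.2 alone, the second may come later. Section 9.1 points to screening, when the second test may not yet have been done. No sentence says which of these governs.

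**The case against.** The strongest reply is that the plan already has the needed controls. The criterion names two tests, and the Synopsis (Study Population) enrolls only patients who have completed a transplant arrival visit, so the arrival test should come before the infusion. Section 8, taken at its word, rules out the day -7 and day -3 example because enrollment would wait for the second result. Section 9.1 puts pregnancy results in the screening review. Section 5.2 adds that pregnant patients are generally not accepted for transplant. The lack of a pregnancy row in Appendix A means little by itself, since other standard-care laboratory tests reviewed under Section 9.1 have no row either.

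Much of this stands. A reader might infer that the exclusion depends only on a test that can postdate the dose; the documents do not support that, because of the arrival test. What remains is that the arrival result may be of any age at infusion, and that Section 8 and Section 5.2 give different answers on whether the second result must be available. The transplant clearance safeguard protects against transplant during pregnancy. It can act after the infusion, which comes first.

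A reader might also infer that delayed conditioning makes a late test certain. If conditioning starts 8 or more days after infusion, any test within 7 days of the actual start does follow the dose. But a test timed to the planned start may already have been done, and no section requires a new study eligibility test after a delay. That case cannot be counted as a failure of the exclusion.

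**Conclusion.** The point holds as an unreconciled conflict in timing, not as a missing safeguard. The second test is anchored to conditioning, its window overlaps the infusion window, and no section requires its result to be available and reviewed before VIR-7831 is given. The arrival test limits the consequence but has no stated maximum age at dosing.

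The size is a count: 21 of 49 permitted day pairs put the second test after the infusion, or 28 of 56 if the day conditioning starts is allowed. It is tempting to read 21/49 as a 43% chance. That would need infusion and test days to be uniform and independent. The documents give no such distribution, and a strict reading of Section 8 would make the two dependent. Table 1 projects 20 female participants of 50. The number of child-bearing potential is not given, so the number affected cannot be estimated and may be small.

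Section 7 notes that no PK or immunogenicity data exist at 2,000 mg IV. A reader might take this as evidence of fetal risk; it says nothing on that either way. The point concerns eligibility and safety sequencing only, with no effect on the half-life analysis or the sample size.

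**What to change.** Reconcile the Synopsis exclusion criteria, Section 5.2, Section 6.1, Section 8, Section 9.1 and Appendix A so that the pregnancy check used to apply exclusion 3 is anchored to the VIR-7831 infusion. State the order of test result, chart confirmation and infusion explicitly, and show it in Appendix A. The choice of test and its permitted age are for the investigators to settle; the review asks only that the sections give one answer.

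The cost is a short amendment and one line on the eligibility checklist. The tests are already standard care, so no new procedure is needed. The small downside is that an infusion may occasionally have to wait for a result.
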